9.2.7.6. Other Anticancer or Experimental Therapy

No other approved or investigational anticancer treatment will be permitted during the study treatment period, including chemotherapy, immunotherapy, biological response modifiers, and hormones.

9.2.7.7. Concomitant Radiotherapy

Palliative radiotherapy to specific sites is permitted if considered medically necessary by the treating physician. It is recommended to avoid radiotherapy for at least 5 days after the last dose of NMS-01940153E and to contact the Sponsor. Also, the irradiated area should be as small as possible, and $\leq 25\%$ of the bone marrow reserve (see [Appendix 5](#)). During the period of irradiation and for 2 weeks after, therapy with NMS-01940153E should be withheld. If irradiation-related toxicities (other than xerostomia) have not normalized to pre-irradiation levels after these 2 weeks of rest, the patient should be removed from the study. Irradiated lesions will be followed for disease progression. In case radiotherapy involving $>25\%$ bone

marrow reserve is needed, the patient will be considered as having progressed and should be removed from treatment. During the study, radiotherapy for active brain metastases will represent a progression.

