4.2.2. Secondary Endpoint(s)

- Overall safety profile of NMS-01940153E characterized by type, severity (graded using NCI CTCAE Version 5.0), duration of the adverse events (AEs) and laboratory and ECGs abnormalities, and relationship of the AEs to study treatment in the first and subsequent cycles of therapy.
- Pharmacokinetic parameters of NMS-01940153E and its main metabolite NMS-03593478 in plasma and urine (urine only in Phase I).
- Objective Tumor Response (Partial and Complete Response) as measured by investigator-assessed RECIST 1.1 (Phase I).
- Objective response rate as measured by investigator-assessed mRECIST (Phase II).
- Duration of response (DoR) as measured by investigator-assessed RECIST 1.1. and investigator-assessed mRECIST
- Progression Free Survival, including landmark analyses, as measured by investigator-assessed RECIST 1.1.
- Overall survival (OS).

4.2.3. Exploratory Endpoint:

- Evaluation of AFP plasma levels;
- Evaluation of tumoral and other clinical prognostic features at baseline;
- Assessment of selected molecular alterations in circulating free DNA (cfDNA) at baseline.

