20. Tumor imaging: to be performed at screening, within 28 days from treatment start (in case a tumor imaging is already available in the specified time window, it has not to be repeated); at the end of even months (even cycles) of treatment and at EoT. The EoT assessment is to be performed only if it was not performed in the previous 4 weeks. In patients withdrawn for reasons other than progressive disease (PD), during follow up, tumor assessment should be performed every 2 months, until PD or until a new antitumor therapy starts. On treatment, a time window of -2/+5 days is allowed. Patients with responding tumors (complete or partial response) must have response confirmed by CT scan at least 4 weeks after the 1 st documentation of response. The same method of assessment and technique should be used to characterize and follow the same lesion at screening, during treatment and at EoT. Ct scan is the desirable method for lesion measurement (see Section 11.3.1).
21. BCLC and TNM Staging: TNM and BCLC staging will be requested at enrollment for all patients, including collection of clinical related additional info
22. Survival follow up: post-treatment survival status, including additional information (e.g. new anticancer therapy), will be collected at the 28-days follow up visit and thereafter every 2 months from last treatment administration until death. Telephone contacts are acceptable for these assessments.
23. Biomarkers sampling: peripheral blood samples will be collected at Enrollment (≤ 7 days before Cycle1 Day1) for analysis of selected molecular alterations in circulating free DNA (cfDNA) from plasma
24. PK blood sample: during the Phase II, a sparse sampling procedure will be adopted; blood sampling for PK is to be performed at cycles 1, 2, 3 and 4 (refer to Table 5 for details).
25. End of Treatment (EoT): visit to be performed within 7 days from the decision of discontinuing the study drug.
26. Off treatment assessments: 28 days, and no more than 35 days, after discontinuation of study treatment patients will return for the following assessments: ECOG PS, blood pressure and heart rate, hematology, blood chemistry, coagulation, concomitant medications, adverse events and survival follow up. Further follow up contacts will be scheduled every 2 months from last treatment administration, until death, to assess the survival status, including possible additional information.

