11.3.1.4. Target Lesions Tumor Response

Complete response (CR) is defined as disappearance of all target lesions and reduction in short axis to <10 mm of any pathological lymph nodes (whether target or non-target).

Partial response (PR) is defined as at least 30% decrease in the sum of the diameters of the target lesions, taking as a reference the baseline sum diameters.

Progressive disease (PD) is defined as at least 20% increase in the sum of diameters of target lesions, taking as reference the smallest sum on study (this includes the baseline sum if that is the smallest on study). In addition to the relative increase of 20%, the sum must also demonstrate an absolute increase of at least 5 mm. (Note: the appearance of one or more new lesions is also considered progression).

Stable Disease (SD) is defined as neither sufficient shrinkage to qualify for PR nor sufficient increase to qualify for PD, taking as reference the smallest sum diameters while on study.

According to mRECIST treatment response for target lesions will be defined as follows:

CR: the disappearance of any intratumoral arterial enhancement in all target lesions.

PR: at least a 30% decrease in the sum of diameters of viable (contrast enhancement in the arterial phase) target lesions, taking as reference the baseline sum of the diameters of target lesions.

PD: an increase of at least 20% in the sum of the diameters of viable (enhancing) target lesions, taking as reference the smallest sum of the diameters of viable (enhancing) target lesions recorded since the treatment started. To note that, consistent with RECIST and mRECIST criteria, only radiographic progression, not clinical progression, determines the calculation of RECIST PD or mRECIST PD. SD: any cases that do not qualify for either partial response or progressive disease.

Since for HCC the measurement of the longest diameter of the viable tumor may be challenging in lesions showing partial internal necrosis, according to mRECIST, the following points should be taken into account in such cases:

- The measurement of the viable tumor should be performed on CT or MRI obtained in the arterial phase, when the contrast between viable vascularized tumor tissue and non enhancing necrotic tissue is the highest.
- The longest diameter of the viable tumor is not necessarily located in the same scan plane in which the baseline diameter was measured: a thorough careful evaluation of the CT or MRI scans is required.

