Appendix 5. The Distribution of Active Bone Marrow in the Adult

Site	Marrow Weight (g)	Fraction Red Marrow - Age 40	Red Marrow Weight -Age 40 (g)	% Total Red Marrow
Head				
Cranium	165.8	0.75	136.6	
Mandible	16.4	0.75	124.3	
			12.3	
Upper Limb Girdle			86.7	
2 Humerus, head & neck	26.5	0.75	20.0	
2 Scapulae	67.4	0.75	50.5	
2 Clavicles	21.6	0.75	16.2	
Sternum	39.0	0.6	23.4	2.3
Ribs			82.6	
1 pair	10.2	All 0.4	4.1	
2	12.6		5.0	
3	16.0		6.4	
4	18.6		7.4	
5	23.8		9.5	
6	23.6		9.4	
7	25.0		10.0	
8	24.0		9.6	
9	21.2		8.5	
10	16.0		6.4	
11	11.2		4.5	
12	4.6		1.8	
Vertebrae (Cervical)			35.8	3.4
1	6.6	All 0.75	5.0	
2	8.4		6.3	
3	5.4		4.1	
4	5.7		4.3	
5	5.8		4.4	
6	7.0		5.3	
7	8.5		6.4	
Vertebrae (Thoracic)			147.9	14.1
1 pair	10.8	All 0.75	8.1	
2	11.7		8.8	
3	11.4		8.5	
4	12.2		9.1	
5	13.4		10.1	
6	15.3		11.5	
7	16.1		12.1	
8	18.5		13.9	
9	19.7		14.8	
10	21.2		15.9	
11	21.7		16.3	
12	25.0		18.8	
Vertebrae (Lumbar)			114.1	10.9
1 pair	27.8	All 0.75	20.8	
2	29.1		21.8	
3	31.8		23.8	
4	32.1		24.1	
5	31.4		23.6	
Sacrum	194.0	0.75	145.6	13.9
Lower limb girdle			273.0	26.1
2 os coxae	310.6	0.75	233.0	
2 femoral head & neck	53.0	0.75	40.0	
Total	1497.7		1045.7	100.0

R.E. ELLIS - The Distribution of Active Bone Marrow in the Adult. Phy. Med. Biol. 5, 255 – 258, 1961.

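### Protocol 9.2.7.7 declares progression from a radiotherapy decision, against the radiographic-only definition of PD, and neither document says which governs PFS and DoR

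*Protocol*

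**What the plan says.** Protocol 9.2.7.7 (Concomitant Radiotherapy) permits palliative radiotherapy to limited fields, and for those patients "Irradiated lesions will be followed for disease progression". When more than 25% of the marrow reserve would be irradiated, "the patient will be considered as having progressed" and is to leave treatment. The section then adds that "radiotherapy for active brain metastases will represent a progression". Neither of these last two sentences mentions a scan, a new lesion or a change in measurements.

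Protocol 11.3.1.4 says that "only radiographic progression, not clinical progression, determines the calculation of RECIST PD or mRECIST PD". Protocol 4.2.2 lists "Progression Free Survival, including landmark analyses, as measured by investigator-assessed RECIST 1.1" as a secondary endpoint, and DoR by both RECIST 1.1 and mRECIST.

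On imaging after treatment, footnote 20 of the schedule of events reads: "In patients withdrawn for reasons other than progressive disease (PD), during follow up, tumor assessment should be performed every 2 months", until PD or a new antitumor therapy. Protocol 11.3.1 repeats this. Section 10 follows patients for progression after treatment only if they have not already progressed.

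SAP 9.7.2 analyses DoR, PFS and OS but does not define the events. SAP 8.2 and 9.7 place event dates and censoring rules in a separate mock-ups and algorithms appendix, which is not in the package.

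**The concern.** One section of the protocol declares progression from a treatment decision, while another says that only imaging can establish it. A patient with stable or responding disease who needs a large palliative field could be recorded as progressed by one site and as a withdrawal without PD by another.

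Two things are at stake. The first is coding: whether PFS and DoR end on the radiotherapy date. That can be settled at analysis, provided the rule is written down. The second is conduct: a site that regards the patient as progressed has no instruction to go on scanning. A later RECIST PD date would then not exist, and no censoring rule could recover it.

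**Working it through.** No stated figure is in dispute, so the main check is to compare the texts.

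**1. Declaration against definition.** RECIST PD in 11.3.1.4 to 11.3.1.6 needs one of three findings: a 20% rise in the target sum with at least 5 mm absolute growth, unequivocal non-target progression, or a new lesion. The marrow sentence in 9.2.7.7 needs none of them. It states two consequences, progression and removal, so it does not read as a stopping rule alone.

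The brain-metastasis sentence conflicts less in practice. Known brain metastases are excluded at entry (exclusion criterion 8), so a brain lesion found on study would normally be a new lesion, and therefore PD, under 11.3.1.6. What stays open there is mainly the date: the scan or the radiotherapy.

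**2. Does any text settle it?** Section 11.3.1.10 treats global deterioration as a reason for stopping and not as an objective response status, and asks sites to go on seeking objective progression. That applies here only by analogy. Section 10 lists a stopping reason other than PD that refers to 9.2.7 (a medical event requiring unauthorised concomitant treatment), but does not link it to the marrow rule. The SAP sections provided are silent.

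**3. Consequences under each reading.**
- *Deemed progression coded as PD:* PFS and DoR end on a non-radiographic date. The two-monthly scans are no longer required. An end-of-treatment scan is still due unless one was done in the previous 4 weeks.
- *Radiographic rule governs:* the patient left for a reason other than PD, scans continue, and PFS and DoR remain radiographic. The exception is if the radiotherapy counts as new antitumor therapy, which would itself end follow-up imaging. SAP 9.5 lists new radiotherapies after treatment among new anticancer therapies and procedures but does not say what follows for imaging or censoring.

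**4. What the trigger measures.** Red-marrow weights are from Protocol Appendix 5 (total 1045.7 g); share = weight / 1045.7.

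| Field | Weight (g) | Share |
|---|---|---|
| Both os coxae | 233.0 | 22.3% |
| Lumbar + sacrum | 114.1 + 145.6 = 259.7 | 24.8% |
| Thoracic + lumbar | 147.9 + 114.1 = 262.0 | 25.05% |
| "Lower limb girdle" (os coxae + femoral head and neck) | 273.0 | 26.1% |

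The trigger depends on field extent, not tumor change. The thoracic-plus-lumbar case is too close to call: the printed percentages give 14.1 + 10.9 = 25.0, which is not above 25%. The safer contrast is 22.3% against 26.1%.

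**5. Size.** Phase II time-to-event endpoints use the Evaluable Set, planned at 38. (That figure reproduces: with an exact one-sided 95% lower limit at an ORR of 0.30, the distance at n = 38 is 0.1197, within the planned 0.12.) One patient is 1/38 = 2.6% of the PFS set. At the assumed ORR there are 0.30 × 38 = 11.4, or about 11, responders, so one responder is about 1/11 = 9% of the DoR set. The documents give no frequency for such radiotherapy. Assuming 0 to 2 patients, between 0 and 2/38 = 5.3% of the PFS set is affected.

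**The case against.** The strongest reply is that 9.2.7.7 belongs to the concomitant-therapy rules, while 11.3.1.4 speaks directly to how PD is determined and so already governs the endpoints. The unseen appendix may say so. This is a fair reading, and it means that an effect on PFS and DoR is not established. It does not settle conduct: an analysis appendix does not tell sites whether to keep scanning, and the protocol makes scanning depend on whether the patient has progressed.

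It can also be said that the PD date is not necessarily lost. That stands in part: an end-of-treatment scan may be due, and 11.3.1 asks for a scan at clinical deterioration. Neither replaces serial follow-up to a later RECIST PD.

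Third, crossing 25% takes several marrow regions or the whole lower limb girdle; the entire lumbar spine is 10.9% and the sacrum 13.9%. Such fields may be rare or absent, any cut-off separates near-equal values, and PFS and DoR are descriptive secondary endpoints in a single-arm trial. All of this stands and limits the weight of the point.

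A reader might also infer that the rule lowers the primary ORR by turning an unconfirmed PR into a non-response. The documents do not support that as a main argument. Section 11.3.1.10 counts best response only until the end of treatment, so a patient removed before confirmation can lose the response under either reading, and relabelling the exit would not restore it.

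**Conclusion.** The conflict is real. Section 9.2.7.7 declares progression without an imaging criterion, 11.3.1.4 excludes that for RECIST and mRECIST PD, and nothing in the package says which prevails. The effect on PFS and DoR is conditional: it arises only if the deemed progression is coded as PD, or if a site stops scanning because of it. A reader might conclude that these endpoints already depend on the size of the radiation field. The texts leave that undetermined.

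The expected effect is small: 2.6% of the PFS set per affected patient, with 0 to 2 patients as an assumption. The purpose of the marrow limit is not stated, and its clinical merit is not judged here. The point deserves correction because the change is cheap and missed scans cannot be recovered.

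**What to change.** Reconcile Protocol 9.2.7.7, 11.3.1 and 11.3.1.4 with SAP 9.7.2 and its algorithms appendix:

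- For both sentences in 9.2.7.7, record the event as a reason for ending treatment, where treatment ends, and separate it from endpoint status.
- State that PD for BOR, DoR and PFS requires RECIST 1.1 criteria, or mRECIST criteria for mRECIST DoR, dated by the scan.
- State that these patients stay in two-monthly imaging until RECIST PD or new antitumor therapy, as footnote 20 already provides for withdrawals without PD.
- State whether this palliative radiotherapy counts as new antitumor therapy, and how it is handled in censoring. Without this, the imaging instruction could lapse on the day radiotherapy starts.

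The marrow threshold and the removal from treatment are not changed. The cost is a few sentences across the two documents and a few follow-up scans of a kind already foreseen. No extra patients are needed. The change will not recover responses left unconfirmed when treatment ends; that depends on the best-response window.

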10. SUBJECT WITHDRAWAL FROM STUDY PARTICIPATION

Patients may withdraw from the study at any time at their own request, or they may be withdrawn at any time at the discretion of the Investigator or Sponsor for safety, behavioral, or administrative reasons.

If the patient does not return for a scheduled visit, every effort should be made to contact him/her. In any circumstance, every effort should be made to document patient outcome, if possible. The Investigator should inquire about the reason for withdrawal, request the patient to return for a final visit, if applicable, and follow-up with the patient regarding any unresolved adverse events.

If the patient withdraws consent for disclosure of future information, no further evaluations should be performed and no additional data should be collected. The Sponsor may retain and continue to use any data collected before such withdrawal of consent.

Patients may continue with therapy unless any of the following occurs:

- Disease progression by RECIST 1.1 at any time, unless there is reasonable evidence of clinical benefit to justify continuation on treatment, to be discussed with the Sponsor;
- Unacceptable drug-related toxicities incompatible with continuation of treatment with NMS-01940153E according to the judgment of the Investigator, even at a reduced dose;
- Any medical event requiring administration of an unauthorised concomitant treatment if it interferes with the study evaluations and/or if it jeopardises patient's safety (see Section 9.2.7);
- Change in the patient's medical status (including pregnancy) such that the Investigator believes that patient safety may be compromised or that it would be in the best patient's interest to stop treatment;
- Occurrence of permanent or significant incapacity or disability;
- Treatment delay for >1 week from day 28 of any cycle due to treatment related toxicity, unless the investigator believes treatment continuation is in the best patient's interest. In this case a maximum delay of 2 weeks is allowed;
- More than two dose de-escalations required;
- Substantial deviation from specified inclusion or exclusion criteria or non-compliance by the patient with protocol requirements;
- Patient's refusal to continue study treatment;
- Withdrawal of consent;

- Patient lost to follow up;
- Death;
- Study terminated by the Sponsor.

Patients will be withdrawn from the study in case of:

- Withdrawal of consent;
- Patient lost to follow up;
- Death;
- Study terminated by the Sponsor.

Data to be collected for the end of study treatment/withdrawal are described in the Schedule of Events, reported in Section [7](#).

After treatment discontinuation patients will be followed for progression, if not progressed earlier, until the start of a new anticancer therapy, and for survival. Patients will be followed for at least 28 days after the last dose of study drug for adverse events and every 2 months up to death, for secondary efficacy endpoint purpose.

11. ASSESSMENTS

11.1. Timing of Assessments

Section [7 \(SCHEDULE OF EVENTS\)](#) summarizes information on the timing of study assessments to be performed during Phase I and Phase II. Protocol waivers or exemptions are not allowed.

11.2. Disease Assessments

11.2.1. TNM Staging

TNM Staging will be performed at enrollment according to “American Joint Committee on Cancer (AJCC) TNM Staging for Hepatocellular Cancer (8th ed., 2017)” [\[18\]](#);

Histological grading and fibrosis score, as defined by Ishak, will be requested, if available.

Table 7. Definitions for T, N, M

T	Primary Tumor
TX	Primary tumor cannot be assessed
T0	No evidence of primary tumor
T1	Solitary tumor ≤ 2 cm, or >2 cm without vascular invasion
T1a	Solitary tumor ≤ 2 cm
T1b	Solitary tumor >2 cm without vascular invasion
T2	Solitary tumor >2 cm with vascular invasion, or multiple tumors, none >5 cm
T3	Multiple tumors, at least one of which is >5 cm
T4	Single tumor or multiple tumors of any size involving a major branch of the portal vein or hepatic vein, or tumor(s) with direct invasion of adjacent organs other than the gallbladder or with perforation of visceral peritoneum
N	Regional Lymph Nodes
NX	Regional lymph nodes cannot be assessed
N0	No regional lymph node metastasis
N1	Regional lymph node metastasis
M	
M0	No distant metastasis
M1	Distant metastasis

11.2.2. Barcelona Clinic Liver Cancer (BCLC) Staging System

BCLC [\[19\]](#) ([Table 8](#)) will be collected at enrollment:

Table 8. Definitions for prognostic groups

Very early stage (0)	
 • Single ≤ 2 cm • Preserved liver function, PS 0
Early stage (A)	
 • Single, or ≤ 3 nodules each ≤ 3 cm • Preserved liver function, PS 0
Intermediate stage (B)	
 • Multinodular • Preserved liver function, PS 0
Advanced stage (C)	
 • Portal invasion and/or extrahepatic spread • Preserved liver function, PS 1-2
Terminal stage (D)	
 • Any tumor burden • End stage liver function, PS 3-4

Additional info on tumoral characteristic will be requested when available.

11.3. Efficacy Assessments

The determination of antitumor efficacy will be based on objective tumor assessments made according to RECIST guideline (version 1.1) [17] and to the modified Response Evaluation Criteria in Solid Tumors (mRECIST) guideline [20].

A summary of RECIST 1.1 and mRECIST is reported in the following sections.

11.3.1. Tumor Imaging

Baseline tumor imaging (by CT scan, PET or MRI) has to be performed at screening within 28 days prior to the treatment start. On treatment, tumor assessments will be performed every even month (i.e., end of Cycle 2, 4, 6 etc) or whenever a clinical deterioration is observed and at the end of last cycle, unless a tumor assessment was performed within the previous 4 weeks. In patients withdrawn for causes other than disease progression, during follow up, regular tumor imaging assessments will be performed every 2 months, until PD or until a new antitumor therapy starts. On treatment, a time window of -2/+5 days is allowed.

Patients with responding tumors (complete or partial response) must have response confirmed at least 4 weeks after the first documentation of response.

CT scan is the desirable method for lesion measurement. MRI is acceptable provided that the size of the measurable lesion is twice the slice thickness of the MRI. MRI should be performed at pre-treatment in case of known or suspected CNS involvement.

According to RECIST, the same method and technique (CT scan or MRI) should be used to characterize each identified and reported lesion at baseline and during the following assessments.

Imaging-based evaluation should be preferred to clinical examination when both could be used to assess the antitumor effect of the treatment.

According to mRECIST, tumor assessment should be performed with the administration of intravenous contrast to obtain a dual-phase imaging of the liver. To prevent possibly allergic reactions to intravenous Contrast Medium (CM), patients with previous reaction(s) to CM, asthma even drug controlled and/or food or drug allergies will be treated with a premedication (corticosteroid).

Patients can be followed with either contrast-enhanced spiral CT (preferably with use of multi-slice scanners) or contrast-enhanced dynamic MRI. Each modality has advantages and disadvantages, and mRECIST does not recommend one modality over another.

However, it is recommended that the same imaging modality be used throughout the study. Ultrasound – including contrast-enhanced ultrasound – is not recommended for the general use of mRECIST.

PET/CT is not accepted for treatment assessment in guidelines.

Obtaining a pre-contrast scan is useful but not mandatory for CT. Conversely, establishing the intrinsic T1 intensity of tumour lesions at baseline is recommended in MRI, in order to infer subsequent contrast enhancement or perform subtraction imaging.

The administration of intravenous contrast is required for all CT or MRI studies if not medically contraindicated. In contrast-enhanced studies, it is crucial to time the contrast administration so that high-quality arterial-phase imaging is obtained on the first run, and high-quality portal venous-phase imaging is obtained on the second run. An arterial phase that is acquired too early (i.e., when the hepatic arterial branches are fully enhanced but the portal vein is not yet enhanced) may be inadequate since the degree of enhancement of HCC is usually higher in the late arterial phase (i.e., when the hepatic arterial branches are fully enhanced, the portal vein is also enhanced, but the hepatic veins are not yet enhanced).

Delayed imaging acquired two to five minutes after injection may be useful, but it is not mandatory and should be done only if it is part of clinical practice. In MRI studies, when using a hepatobiliary contrast agent instead of an extracellular contrast agent, the hepatobiliary phase acquired about 20 min after injection of gadoxetate disodium may be used to aid lesion detection and diagnostic confidence [20].

All patients' files and scans must be available for source verification.

